11.2.6.3. Discontinuation-Emergent Signs and Symptoms (DESS) Scale

The DESS Scale (Rosenbaum-1998) is a clinician-rated instrument of 43 items used to evaluate signs and symptoms associated with discontinuation or interruption of monoamine reuptake inhibitor treatment.

On non-clinic days, the DESS Scale will be completed by site staff during a call to the subject.

11.2.6.4. Hamilton Anxiety Rating Scale (HAM-A)

The HAM-A is a widely used and well-validated tool for measuring the severity of a patient's anxiety. It should be administered by an experienced clinician. The HAM-A consists of 14 items, each defined by a series of symptoms, and measures both psychic anxiety (mental agitation and psychological distress) and somatic anxiety (physical complaints related to anxiety). Each item is scored on a 5-point scale, ranging from 0 = not present to 4 = severe.

The Structured Interview Guide for the HAM-A (SIGH-A) will be used for the administration of the HAM-A.

11.2.6.5. Montgomery-Asberg Depression Rating Scale (MADRS)

The Montgomery-Asberg Depression Rating Scale (MADRS) is a widely used clinician-rated assessment of the subject's level of depression. The measure contains 10 items that measure apparent and reported sadness, inner tension, reduced sleep and appetite, difficulty concentrating, lassitude, inability to feel, and pessimistic and suicidal thoughts. Each item is scored in a range of 0 to 6 points, with higher scores indicating increased depressive symptoms.

The Structured Interview Guide for the MADRS (SIGMA) will be used for the administration of the MADRS.

11.3. Effectiveness Assessments

11.3.1. Eating Disorder Examination Questionnaire (EDE-Q) Modified

The Eating Disorder Examination Questionnaire (EDE-Q) is a self-report version of the eating disorder examination (EDE) (Fairburn-1994). Like the EDE, the EDE-Q measures eatingdisorder psychopathology in the past 28 days, and over longer intervals for diagnostic items. The EDE-Q yields scores on the same subscales (dietary restraint, eating concern, weight concern, and shape concern), global score, and binge-eating frequency variables as the EDE interview. Research with clinical samples of patients with BED has reported acceptable agreement between the EDE-Q and EDE interview (Grilo-2001A; Grilo-2001B). Convergent findings from confirmatory factor analyses of item data obtained from patients with BED (Grilo-2010) and patients with overweight/obesity (Grilo-2012; Grilo-2013; Hrabosky-2008) as well as non-clinical groups (Grilo-2015) support an alternative, brief version of the EDE-Q and EDE comprising 7 items to generate a global score and 3 subscales (dietary restraint, shape/weight overvaluation, and body dissatisfaction) referred to as the EDE-Q7 (Grilo-2015). In the present study, the EDE-Q7 along with 3 items to assess binge eating, including the number of binge eating days will be used and referred to as the EDE-Q modified.

11.3.2. Sheehan Disability Scale (SDS)

The SDS was developed to assess functional impairment in 3 domains: work/school, social, and family life. The subject rates the extent to which work/school, social life, and home life have been impaired by his/her symptoms on an 11-point visual analog scale. The 3 items can be summed into a single global measure of impairment that ranges from 0 (unimpaired) to 30 (highly impaired). This anchored visual analog scale uses spatiovisual, numeric, and verbal descriptive anchors simultaneously to assess disability across 3 domains: work; social life, and family life. There are verbal descriptors for the points on the scale as well as numerical scores that provide more precise levels of the verbal descriptors. The SDS takes approximately 10 minutes to complete.

11.3.3. Binge-eating Clinical Global Impressions–Severity of Illness (BE-CGI-S)

The BE-CGI-S (Busner & McElroy, 2012; based on Guy-1976) asks the clinician one question: "Considering your total clinical experience with the adult Binge Eating Disorder (BED) population, how mentally ill is the subject at this time?" The clinician's answer is rated on the following 7-point scale: 1 = normal, not at all ill; 2 = borderline mentally ill; 3 = mildly ill; 4 = moderately ill; 5 = markedly ill; 6 = severely ill; 7 = among the most extremely ill subjects.

This rating is based upon observed and reported BED symptoms, behavior, and function in the past 7 days. Clearly, symptoms and behavior can fluctuate over a week; the score should reflect the average severity level across the 7 days.

11.4. Other Assessments and Scales

11.4.1. Short Form-12 Health Survey (SF-12)

The SF-12 is a 12-item self-report questionnaire that is a subset of the SF-36 Health Survey. The survey captures physical and mental health. There are 8 subscales including: Physical functioning, Role-physical, Bodily pain, General health, Vitality, Social Functioning, Role-emotional, Mental health. The responses are reported on a 3 or 5 point Likert scale, depending on the question. The SF-12 is collected only for subjects enrolling in this study after completing Study SEP360-221.

11.5. Study Visits and Assessments

11.5.1. Open-label Baseline: Visit 1E (Day -1)

Subjects will be evaluated at the Open-label Baseline Visit to determine their eligibility to enroll in the study. The following study-related procedures will be performed at Open-label Baseline:

Confidential and Proprietary

- Obtain informed consent
- Review inclusion/exclusion criteria
- Demographics
- Administer EDE-Q modified (Subjects from Study SEP360-221 only)
- Dispense study drug (First dose taken the following day on Day 1)

Results for the following study-related procedures will be carried over from the core study Week 12 visit, and do not need to be performed for the Open-label Baseline visit:

- Physical and neurological examinations
- Vital signs, weight, and BMI
- ECG
- Scales: BE-CGI-S, SDS, SF-12 (Subjects from Study SEP360-221 only), C-SSRS, HAM-A, MADRS, and EDE-Q modified (Subjects from Study SEP360-321 only)
- Clinical laboratories (serum chemistry, lipid panel, hemoglobin A1c, hematology, urinalysis), UDS, and urine pregnancy test for females of child bearing potential
- Breath alcohol test

AEs and concomitant medications ongoing at the Week 12 visit in the core study will be carried over. Other data such as height will be carried over from other visits in the core study.

Further information on data carried over from the core study will be addressed in the DMP.

11.5.2. Treatment Period (Visits 2E – 15E; Weeks 2 – 52)

Approximate midpoint between monthly Visits 3E and 4E, Visits 4E and 5E, Visits 5E and 6E, Visits 6E and 7E, Visits 7E and 8E, Visits 8E and 9E, Visits 9E and 10E, Visits 10E and 11E, Visits 11E and 12E, Visits 12E and 13E, Visits 13E and 14E, and Visits 14E and 15E (ie, 14 ± 2 days after visit) a member of the study site staff will contact the subject/parent/legal guardian via telephone, text, or email between monthly visits according to the timeline in Table 2. These contacts will be used to collect AEs, and concomitant medications, as well as to remind subjects about adherence to study drug administration and upcoming visits, following which an unscheduled visit may be scheduled, if necessary. The date and time of these contacts will be documented in the CRF.

11.5.2.1. Visit 2E: Week 2 (Day 14 ± 3)

The following study related procedures will be performed:

- Record concomitant medications
- Collect vital signs and weight
- Record AEs
- Administer C-SSRS

- Perform study medication accountability
- Dispense study medication

11.5.2.2. Visit 3E (Week 4; Day 28 ± 3), Visit 5E (Week 12; Day 84 ± 3), Visit 7E (Week 20 Day 140 ± 3), Visit 9E (Week 28; Day 196 ± 3), Visit 11E (Week 36; Day 252 ± 3), and Visit 13E (Week 44 Day 308 ± 3)

The following study related procedures will be performed:

- Record concomitant medications
- Collect vital signs and weight
- Perform physical examination (Visit 5E, Week 12, only)
- Perform ECG (Visit 3E, Week 4; Visit 5E, Week 12; and Visit 11E, Week 36 only)
- Record AEs
- Administer Scales:
- EDE-Q modified, SDS (Visit 5E, Week 12; and Visit 11E, Week 36, only), C-SSRS, BE-CGI-S, and SF-12 (Visit 5E, Week 12; and Visit 11E, Week 36 only; Subjects from Study SEP360-221 only)
- Collect samples for clinical laboratories (serum chemistry, lipid panel, hemoglobin A1c, hematology, urinalysis) (Visit 5E, Week 12; and Visit 11E, Week 36 only)
- Collect samples for UDS and urine pregnancy test for females of child bearing potential
- Perform breath alcohol test
- Perform study medication accountability
- Dispense study medication
- 11.5.2.3. Visit 4E (Week 8; Day 56 ± 3), Visit 6E (Week 16; Day 112 ± 3), Visit 8E (Week 24; Day 168 ± 3), Visit 10E (Week 32; Day 224 ± 3), Visit 12E (Week 40; Day 280 ± 3), and Visit 14E (Week 48; Day 336 ± 3)

The following study related procedures will be performed:

- Record concomitant medications
- Collect vital signs and weight
- Perform physical examination (Visit 8E, Week 24, only)
- Perform neurological examination (Visit 8E, Week 24, only)
- Perform ECG (Visit 8E, Week 24, only)
- Record AEs

- Administer Scales: SDS (Visit 8E, Week 24, only), EDE-Q modified, C-SSRS, BE-CGI-S, SF-12 (Visit 8E, Week 24, only; Subjects from Study SEP360-221 only), HAM-A (Visit 8E, Week 24, only), and MADRS (Visit 8E, Week 24, only)
- Collect samples for clinical laboratories (serum chemistry, lipid panel, hemoglobin A1c, hematology, urinalysis) (Visit 8E, Week 24, only)
- Collect samples for urine pregnancy test for females of child bearing potential (Visit 12E, Week 40 and Visit 14E, Week 48 only)
- Perform study medication accountability
- Dispense study medication

11.5.2.4. Visit 15E/End of Treatment (Week 52; Day 364 ± 1)

The following study related procedures will be performed:

- Record concomitant medications
- Perform physical and neurological examinations
- Collect vital signs and weight
- Perform ECG
- Record AEs
- Administer Scales: EDE-Q modified, SDS, MADRS, C-SSRS, BE-CGI-S, SF-12 (Subjects from Study SEP360-221 only), HAM-A, CSSA, and DESS
- Collect Samples for clinical laboratories (serum chemistry, lipid panel, hemoglobin A1c, hematology, urinalysis), UDS and urine pregnancy test for females of child bearing potential
- Perform breath alcohol test
- Perform study medication accountability

11.5.3. Withdrawal Period

All subjects, including those who complete treatment and those who discontinue treatment, will complete weekly in-clinic visits during the 3 week study medication withdrawal period. In addition to the weekly visits, the CSSA and DESS will be completed during the 3 week study medication withdrawal period on non-clinic visit days. Clinical site staff will call the subject every other day during the study medication withdrawal period, beginning the second day after the last dose of study drug, unless a clinic visit is scheduled for that day (up to 3 times per day if the clinical site staff are unable to contact the subject on the first 2 attempts). Clinical site staff will record the responses to the CSSA and DESS in the subject's source information and in the CRF with the contact date and time. During these calls, clinical site staff will also record AE(s) and concomitant medications.

A window of ± 1 day will be allowed for each weekly clinic visit and telephone call. If the subject cannot be contacted on a given day, during the next contact the study site staff will

retrospectively collect the missed CSSA and DESS, in addition to the current day's CSSA and DESS, as necessary.

11.5.3.1. Visit 16E (Week 53; Day 371 ± 1^5) and Visit 17E (Week 54; Day 378 ± 1^6)

The following study related procedures will be performed:

- Record concomitant medications
- Collect vital signs and weight
- Perform ECG
- Record AEs
- Administer Scales: MADRS, C-SSRS, BE-CGI-S, HAM-A, CSSA, and DESS

11.5.3.2. Visit 18E/End of Study (Week 55; Day 385 ± 1^7)

The following study related procedures will be performed:

- Record concomitant medications
- Perform physical and neurological examinations
- Collect vital signs and weight
- Perform ECG
- Record AEs
- Administer Scales: MADRS, C-SSRS, BE-CGI-S, HAM-A, CSSA, DESS, SDS, SF-12 (Subjects from Study SEP360-221 only)
- Collect Samples for clinical laboratories (serum chemistry, lipid panel, hemoglobin A1c, hematology, urinalysis), UDS, and urine pregnancy test for females of child bearing potential
- Perform breath alcohol test

Confidential and Proprietary

⁵ For Early terminating subjects 7 days post last dose ± 1 day

 $^{^6}$ For Early Terminating subjects 14 days post last dose \pm 1 day

 $^{^7}$ For Early Terminating subjects 21 days post last dose \pm 1 day

12. SAFETY REPORTING

12.1. Definitions

12.1.1. Adverse Events

An AE is any untoward medical occurrence in a study subject administered a medicinal (investigational) product and which does not necessarily have a causal relationship with this treatment.

An AE can, therefore, be any unfavorable and unintended sign (including an abnormal laboratory finding), symptom, or disease occurring after the administration of a medicinal (investigational) product, whether or not considered related to the medicinal (investigational) product. AEs may include the onset of new illness and the exacerbation of pre-existing conditions. AEs will be collected from the time the informed consent is obtained to the last study visit.

Lack of effectiveness may be an expected potential outcome and should not be reported as an AE unless the event is unusual in some way.

New signs and symptoms of underlying disease, or signs and symptoms of emerging disease must be recorded as AEs.

The Investigator should attempt to establish a diagnosis of the event based on signs, symptoms, and/or other clinical information. In such cases, the diagnosis should be documented as the AE and not the individual signs/symptoms.

12.1.2. Serious Adverse Events

A serious adverse event (SAE) is an AE that meets one or more of the following criteria:

- Results in death
- Is life-threatening (ie, a patient is at immediate risk of death at the time of the event, not an event where occurrence in a more severe form might have caused death)
- Requires hospitalization or prolongation of existing hospitalization
- Results in persistent or significant disability or incapacity
- Is a congenital anomaly or birth defect
- Is an important medical event that may jeopardize the subject or may require an medical or surgical intervention to prevent one of the outcomes listed above. Examples of such medical events include allergic bronchospasm requiring intensive treatment in an emergency room or at home, blood dyscrasias or convulsions that do not result in inpatient hospitalization

The term "severe" is often used to describe the severity of a specific event (as in mild, moderate, or severe myocardial infarction) (see Section 12.3); the event itself, however, may be of relatively minor medical significance (such as severe headache). This is not the same as

"serious," which is based on subject/event outcome or action criteria usually associated with events that pose a threat to a subject's life or functioning as defined by the criteria above.

During the study, if a subject has a hospitalization or procedure (eg, elective surgery) that was scheduled before the study entry, ie, before informed consent for an event/condition that occurred before the study, the hospitalization is considered a therapeutic intervention and not the result of a SAE. However, if the event/condition worsens during the study, it should be reported as an AE (or SAE, if the event/condition results in a serious outcome such as prolongation of hospitalization).

Life-threatening means that the subject was, in the view of the Investigator, at immediate risk of death from the event as it occurred. This definition does not include an event that had it occurred in a more severe form might have caused death.

12.2. Objective Findings

Clinically significant abnormal objective findings (eg, clinical laboratory value, ECG value, and physical examination observation) will also be recorded as AEs.

When a clear diagnosis is available that explains the objective findings, this diagnosis will be recorded as the AE, and not the abnormal objective finding (eg, viral hepatitis will be recorded as the AE, not transaminase elevation). If a definite diagnosis is not available, then record the sign (eg, clinically significant elevation of transaminase levels) or symptom (eg, abdominal pain) as the AE.

Clinical laboratory test results will be reviewed by the Investigator. The Investigator must determine the clinical significance of all out of range values. Clinical laboratory test with possibly drug-related or clinically relevant abnormal values of uncertain causality may be repeated. Any abnormal values that persist should be followed at the discretion of the Investigator. Laboratory reports will be initialed and dated on all pages by the Investigator.

Clinical Laboratory Tests Outside the Normal Range: Any value outside the normal range will be flagged for the attention of the Investigator or appropriate designee at the site. The Investigator or appropriate designee will indicate whether or not the value is of clinical significance. If the result of any test (or repeat test, if done) from the samples taken at OL Baseline is indicated as clinically significant and is not covered by the inclusion criteria in Section 8.1, the subject will **not** be allowed into the study. Additional testing during the study may be done if medically indicated. If a clinically significant abnormality is found in the samples taken after dosing, during the study, and/or at the Follow-up Visit, this should be recorded as an AE and the subject will be followed until the test(s) has (have) normalized or stabilized.

All on site ECG tracings and ECG over-read reports will be reviewed by the Investigator. The Investigator must determine the clinical significance of all abnormal ECGs. ECG with possibly drug-related or clinically relevant abnormal findings of uncertain causality may be repeated. Any abnormal ECG that persists should be followed at the discretion of the Investigator. ECG tracings will be initialed and dated on all pages by the Investigator.

12.3. Collection and Recording of Adverse Events

All AEs must be collected and recorded in the subject's study records/source documents, in accordance with the Investigator's normal clinical practice, and on the CRF. All AEs will be followed up until resolution, stabilization of the condition, the event is otherwise explained, or the subject is lost to follow-up.

Each AE is to be evaluated for duration, severity, frequency, seriousness, action taken with the study treatment, outcome, and causal relationship to the study treatment. Definitions for severity, frequency, action taken with the study treatment, outcome, and causal relationship to the study treatment are presented below.

The severity of AE:

- **Mild** Ordinarily transient symptoms that do not influence performance of subject's daily activities. Other treatment is not ordinarily indicated.
- **Moderate** Marked symptoms sufficient to make the subject uncomfortable. Moderate influence on performance of subject's daily activities. Other treatment may be necessary.
- Severe Symptoms cause considerable discomfort. Substantial influence on subject's daily activities. May be unable to continue the study, and other treatment may be necessary.

The frequency of AE:

- **Once** an isolated episode
- Intermittent occurs on 2 or more separate occasions
- **Continuous** does not abate from date of onset to date of resolution

The action taken with the study treatment:

- **Drug Interrupted** Study medication stopped temporarily
- Drug Withdrawn Study medication stopped permanently
- Dose Reduced
- Dose Increased
- Dose not Changed
- Not Applicable

The outcome of the AE:

- Recovered/Resolved
- Recovering/Resolving
- Not Recovered/Not Resolved
- Recovered/Resolved with Sequelae
- Fatal

Confidential and Proprietary

• Unknown

The causal relationship of the AE to the study treatment:

- Not related
 - **Not related** Improbable temporal relationship and is plausibly related to other drugs or underlying disease.
 - **Unlikely** occurred within a reasonable time frame after administration/discontinuation of the study medication, but there is a likely association of an intercurrent/underlying medical condition or other drugs.
- Related.
 - **Possible** occurred in a reasonable time after study-medication administration, but could be related to concurrent drugs or underlying disease.
 - **Probable** occurred in a reasonable time after study-medication administration, is unlikely to be attributable to concurrent drugs or underlying disease, and there is a plausible mechanism to implicate the study medication.
 - **Definite** occurred in a reasonable time after study-medication administration and cannot be explained by concurrent drugs or underlying disease. The AE should respond to dechallenge/rechallenge, however, this is not mandatory before assigning a definite causality.

The Medical Monitor is the initial contact person for protocol-related questions or discussion of AEs. The contact information for the Medical Monitor as well as other emergency contact information can be found in Table 1 of this protocol.

12.4. Immediately Reportable Events

The following medical events must be immediately reported to the Sponsor:

- SAE
- Pregnancy

Emergency contact information can be found in Table 1.

12.4.1. Serious Adverse Event

If the Investigator or study center staff becomes aware of a SAE that occurs in a study subject from the time that informed consent is signed through 30 days following the last dose of the study medication, this must be reported within 24 hours to PPD-PVG, the medical monitor, and Sunovion responsible physician whether considered related or unrelated to the study medication. SAEs occurring from the time of informed consent through 14 days following last dose of the study medication also must be recorded on the CRF and the data recorded should match that on the SAE form.

Following the end of subject participation in the study, the Investigator or an authorized delegate should report SAEs "spontaneously" to PPD-PVG if considered at least possibly related to the study medication.

Confidential and Proprietary

Serious AEs will be followed until resolution, loss to follow-up, stabilization of condition, or the event is otherwise explained.

In addition to the initial notification, an initial SAE form as applicable must be completed and signed and sent via fax or email (see Table 1) to PPD-PVG within 1 business day of the Investigator or study site staff becoming aware of the event. The SAE report form must be signed by the Investigator or appropriate designee. The Sponsor provides the SAE form used to report SAEs.

The Sponsor or designee will promptly notify all study sites and Investigators of a SAE that is determined to be expedited to the Regulatory Authorities in accordance with applicable law(s) and regulation(s). These SAEs must be promptly reported to the Institutional Review Board (IRB) by the Investigator or the appropriate person at the site.

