QRS	Electrocardiographic wave (complex or interval)
QT	Electrocardiographic interval from the beginning of the QRS complex to the end of the T wave
QTc	QT interval corrected for heart rate
RR	RR interval
SAE	Serious adverse event
SAP	Statistical analysis plan
SD	Standard deviation
SDS	Sheehan disability Scale
SERT	Serotonin transporter
SF-12	Medical Outcomes Study 12-Item Short Form
SIGH-A	Structured Interview Guide for the HAM-A
SIGMA	Structured Interview Guide for the MADRS
SNRI	Serotonin norepinephrine reuptake inhibitor
SSRI	Selective serotonin reuptake inhibitor
SOC	System organ class
SOP	Standard operating procedure
TEAE	Treatment-emergent adverse event
t _{max}	Time to maximum concentration
UDS	Urine drug screen
US	United States
USP	United States Pharmacopeia
VAS	Visual analog scale
WBC	White blood cells
WHO-DD	World Health Organization Drug Dictionary

Table 3:List of Abbreviations (Continued)

Terms	Definition of terms
CRF	A printed, optical, or electronic document designed to record all of the protocol required information to report to the Sponsor for each study subject.
Study Drug (or Study medication)	Term to cover investigational drug.
Open-label Treatment Period	The period of the study in which the study drug is administered.
End of Treatment	The day that the subject receives protocol-defined last dose of the study drug.

Table 4:Definition of Key Study Terms

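### Does the 14-day limit in Protocol 12.4.1 leave late serious adverse events off the CRF and out of the discontinuation-emergent tables?

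*Protocol*

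**What the plan says.** Protocol 12.4.1 sets two windows for serious events. SAEs are reported to pharmacovigilance within 24 hours if they occur up to 30 days after the last dose. The next sentence sets the CRF window: "SAEs occurring from the time of informed consent through 14 days following last dose of the study medication also must be recorded on the CRF". It continues with the matching duty: "also must be recorded on the CRF and the data recorded should match that on the SAE form".

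Other sections bear on the same events:

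- Protocol 12.1.1: "AEs will be collected from the time the informed consent is obtained to the last study visit".
- Protocol 12.1.2: "A serious adverse event (SAE) is an AE that meets one or more of the following criteria".
- Protocol 12.3, of all AEs: they "must be collected and recorded in the subject's study records/source documents, in accordance with the Investigator's normal clinical practice, and on the CRF". No end date is given there.
- Protocol 11.5.3, on the withdrawal-period telephone contacts: "During these calls, clinical site staff will also record AE(s) and concomitant medications". The withdrawal visits at Weeks 53, 54 and 55 also list AE recording.
- Protocol 15.3.3.1 and SAP 7.4.2: serious treatment-emergent AEs (TEAEs) run to 14 days after discontinuation of drug. DEAEs run from after the last dose to the Week 55 visit. Serious DEAEs are summarized, and the SAP adds DEAE incidence by withdrawal interval (1-7, 8-14, and 15 days or more).

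**The concern.** Read alone, the 12.4.1 sentence looks like a cut-off. It is specific to SAEs, it follows a 30-day reporting rule, and it does not refer to 12.3. A site could infer that an SAE on Days 15 to 30 goes to pharmacovigilance only.

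A fully dated SAE that starts more than 14 days after the last dose is not a TEAE by onset. Because the AE tables are limited to TEAEs and DEAEs, it can be counted only as a DEAE. If it were missing from the CRF, the serious-DEAE incidence and the last withdrawal interval would be short, and the clinical database would disagree with the SAE reports the sponsor holds. Withdrawal effects are a secondary objective, so those tables matter.

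**Working it through.** **1. The plan's own timing.** End of Treatment is defined in Protocol Table 4 as "The day that the subject receives protocol-defined last dose of the study drug", and its visit is "Visit 15E/End of Treatment (Week 52; Day 364" ± 1). The last visit is Day 385 ± 1, so 385 − 364 = 21 days. This agrees with the 21 ± 1 days after last dose stated for early terminators in the footnote to Protocol 11.5.3.2.

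**2. The nominal mismatch.** The 12.4.1 window ends on Day 364 + 14 = 378. Days 379 to 385 lie beyond it: 7 of 21 days, or 33%.

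| Subjects | Last visit, days after last dose | Days past the 14-day point |
|---|---|---|
| Early terminators | 20 to 22 | 6 to 8 (6/20 = 30% to 8/22 = 36%) |
| Completers, both visit windows moving | 384 − 365 = 19 to 386 − 363 = 23 | 5 to 9 (5/19 = 26% to 9/23 = 39%) |

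**3. The last DEAE interval.** SAP 7.4.2 adds one day when it derives withdrawal duration; SAP 6.1.1.2 counts withdrawal days without it. The SAP does not say which count applies to AE onset. With the extra day, the interval of 15 days or more starts at last dose + 14, and 7 of its 8 days (88%) lie past the 12.4.1 window. Without it, all 7 days do. Either way, nearly all of that interval depends on recording under the general AE rules.

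**4. Do the general rules reach those days?** Take an SAE starting on Day 18 after the last dose in a subject who attends Week 55. It is an AE (12.1.2). It falls within the collection period (12.1.1). All AEs go on the CRF (12.3). Staff ask about AEs at the calls and visits of that week (11.5.3). SAP 7.4.2 likewise expects AE collection to continue to the last visit. CRF entry is therefore required without using 12.4.1.

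**5. What the 14-day sentence adds.** Take a subject whose last visit is 2 days after the last dose and who has an SAE on Day 10. Protocol 13.3 lets subjects leave the withdrawal period for any reason, and SAP 6.1.8 recognizes subjects who never enter it. Collection under 12.1.1 stopped at Day 2, but the event is a serious TEAE, whose window runs to Day 14. The 12.4.1 sentence is what puts it on the CRF. Replacing 14 days with the last study visit would remove that cover.

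**6. Size if sites misread the sentence.** Three inputs are assumptions, not figures from the documents: 200 to 500 subjects reaching the final week (500 is the whole planned enrolment, so a ceiling), 2 to 8 SAEs per 100 person-years, and 10% to 50% of such SAEs omitted.

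- Person-years over 7 days: 200 × 7/365.25 = 3.83; 500 × 7/365.25 = 9.58.
- SAEs in those days: 3.83 × 0.02 = 0.077; 9.58 × 0.08 = 0.767.
- SAEs lost: 0.077 × 0.1 = 0.008; 0.767 × 0.5 = 0.383.
- Chance of losing at least one: 1 − exp(−0.0077) = 0.8%; 1 − exp(−0.383) = 32%.
- Ceiling, a 9-day gap for all 500: 500 × 9/365.25 × 0.08 × 0.5 = 0.49 events; 1 − exp(−0.49) = 39%.

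**The case for a change.** The strongest case for a change is the matching duty. The general rules secure the CRF entry, but they do not say that it must agree with the SAE form. The only sentence that says so carries the 14-day window. Monitoring under Protocol 16.3 compares the CRF with source documents and does not name the SAE form. It can also be said that if 12.3 governs CRF entry, the 14-day figure does no work, so it must have been meant as a limit.

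The second argument fails on step 5 above: the figure does work for subjects who leave early. It acts as a minimum, and the word *also* in the sentence fits that reading.

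The first argument stands in part. No explicit matching duty covers roughly the last week. However, Protocol 16.5 defines source documents broadly enough that a completed SAE form can reasonably be included, which brings it within the 16.3 check. The sponsor receives the SAE report under the 30-day rule in any case, and comparing SAE reports with the clinical database before lock is routine practice. The Data Management Plan, which is not among the documents, may already require that comparison.

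**Conclusion.** The mismatch of dates is real: nominally 7 days, and 5 to 9 days across the visit windows. Its consequence is editorial. Followed as written, the plan puts late-withdrawal SAEs on the CRF and gives sound serious-DEAE counts. Serious-TEAE counts are unaffected, because that window is also 14 days.

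What is left is a missing cross-reference that a careless reader could misconstrue, and a matching duty not spelled out for the last week. Even under misreading, the expected loss is below half an event. That figure rests on the assumed SAE and omission rates, so it indicates scale only. The obvious edit, ending the window at the last study visit, would do more harm than good for subjects who leave before Day 14. A pre-lock comparison of SAE reports with the CRF would only write down ordinary practice. No change to the plan is needed.
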